Efforts to address decisional gaps between System 1 and System 2 thinking in other fields have involved role-playing or games to simulate System 2 thinking states, such as having participants

evaluate their cravings for tobacco during hot state and cold state sessions.^{14,15,23,24} In clinical medicine, simulation has increasingly been used to help health care professionals, alone and in teams, practice how they would handle stressful situations such as cardiac arrest or emergent trauma situations in emergency rooms.²⁵⁻³¹ By extension, these approaches could help address decisional gaps for prescribing high-risk medications for older adults, thereby improving patient safety and welfare.

2. Study Aims

We propose a 2-phase project consisting of provider qualitative interviews and a 2-arm pilot randomized controlled pragmatic trial in which physicians in training (interns) caring for elderly inpatients are assigned to receive simulation training or an educational control. The main goal of this project is to improve patient safety.

The objectives and endpoints for the trial are summarized below.

OBJECTIVES	ENDPOINTS	JUSTIFICATION FOR ENDPOINTS
Primary		
To determine whether simulation-based training reduces the prescribing of high-risk medications to hospitalized older adults.	Number of high-risk medications doses prescribed per day to eligible patients assigned to intervention providers compared with control providers.	This outcome is measurable using electronic health record (EHR) data and will provide evidence of provider behavior change during the follow-up period.
Secondary		
To evaluate whether simulation-based training reduces the continued prescription for high-risk medication to hospitalized older adults at discharge.	Discharge medication order written for one of the eligible high-risk medications to eligible patients assigned to intervention providers versus control providers	This outcome is measurable using EHR data and will provide evidence of whether the intervention results in fewer high-risk medications for patients at discharge.
To determine whether there are impacts of simulation-based training on prescribing of other related medications.	Number of medication doses prescribed per day to eligible patients assigned to intervention providers versus control providers for opioids, trazodone, and melatonin	This outcome is measurable using EHR data and will provide evidence of whether there are spillover effects on other related medications.

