3.2 Overall design

We propose a 2-phase project consisting of provider qualitative interviews and a 2-arm pilot randomized controlled pragmatic trial in which physicians in training (interns) caring for elderly inpatients are assigned to receive simulation training or an educational control.

The first phase, qualitative interviews, are a separate aim from the pragmatic trial and have already been reviewed and approved by the MGB IRB and is governed under a separate protocol (MGB IRB: 2020P002467). This aim consists of brief virtual qualitative interviews with approximately 25 inpatient providers and allied team members (e.g., nurses or pharmacists) to elicit perspectives on prescribing of high-risk medications in the in-patients setting as well as simulation-based training. These interviews are being conducted virtually with providers at other MGB sites and former interns who are no longer part of the general medicine service to avoid contamination with the trial using an MGB-approved video platform. This aim is being used to inform the design of the simulation-based training intervention used

in Aim 2 (pragmatic trial). Providers are identified through referrals by clinicians and recent prescribing history and contacted through email invitation. They are providing verbal consent for their participation and receiving renumeration for their participation. **The remainder of this protocol is about the 2-arm pilot randomized trial.**

The 2-arm pilot randomized controlled trial will determine whether a newly-designed simulation-based training program for providers based on underlying principles of System 1 and System 2 thinking reduces prescribing of high-risk medications for hospitalized older adults versus control, with the ultimate goal of improving patient safety. We will also measure subsequent prescribing for patients cared for by other providers and other adoption and implementation outcomes to explore the extent to which the intervention could be used at scale.

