BWH and BWFH uses 2-week service blocks for its inpatient general medicine evening coverage, and the service overall consists of 6 day and 8 evening (twilight) teams covering geographically distinct wards at 2 hospital sites with daily censuses of 15-20 patients. These teams typically consist of an attending, a resident, an intern (i.e., 1st year of residency), and medical students. There is no cross-coverage across teams. We will focus on interns from the “twilight” (i.e., evening) teams as they cover the shifts during which the high-risk medications of interest (specifically anti-psychotics, benzodiazepines, and sedative hypnotic “Z-drugs”) are typically first initiated and are also the first point of contact for nurses, pharmacists, and other physicians. Given their stage of training and the nature of their workflow, they are also most prone to make decisions using System 1 thinking.

At the beginning of each rotation, we will identify the interns assigned to the twilight teams (i.e., the primary prescriber and responding clinician on the general medicine service team). We will invite these interns to participate in the study via email invitation. Interns who consent will be randomized in a 1:1 ratio with a random number generator to one of 2 arms: (a) Arm 1: simulation intervention and (b) Arm 2: control (online education) intervention. The unit of randomization will therefore be the intern. Randomizing at the intern level will reduce the possibility of contamination across patients. Providers will receive \$25 for completing the initial provider survey, \$75 for completing the intervention or control assignment (e.g., simulation or online education training), and \$50 for completing the endline (follow-up) questionnaire. Other ward staff will be blinded to arm assignment to the extent possible. Data analysts will be blinded to arm assignment. This is a highly feasible approach used by investigators conducting provider-facing intervention trials at BWH.

[figure not shown]

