6.2 Outcomes

The primary outcome will be measured on the patient-level as the number of high-risk medication doses prescribed per day to eligible patients beginning on the day the intervention arms are delivered to both arms until the end of follow-up. We will only measure doses ordered by the interns in the study. As described above, we will censor follow-up time on when patients transition from the intern's service, when the intern transitions off the twilight service, discharge, or in-hospital

death. The interventions in both arms will be delivered on the same day, so there will be no immortal time bias. Medications that are written pro re nata (PRN) will be treated the same as standing orders for the primary analysis. If patients are eligible to be measured for multiple medication classes (i.e., antipsychotics and benzodiazepines/sedative hypnotics), we will sum the medication doses across the classes.

In secondary analyses, we will only measure doses that are standing orders (i.e., not PRN doses) and doses that were actually administered to patients. We chose to measure this outcome on the patient-day level, because this would enable the fairest comparison between the arms, given that patients have variable lengths of stay and, as a result, the lengths of time under the interns' care. These data will be collected through structured EHR data from MGB paired with data collected from the scheduling system.

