7.1 Statistical Hypotheses

Our null hypothesis will be that number of high-risk medication doses prescribed per day to eligible patients assigned to intervention providers will be no different than those in the control arm.

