We will obtain e-consent with a waiver of written consent (signature) and waiver of documentation of informed consent for participation in the trial through e-consent documentation in REDCap, a secure HIPAA-compliant web-based platform hosted on our Mass General Brigham servers. Intern physician subjects will be invited to participate via email. The information sheet below will be attached to the email, and contains information about the study, their participation, and the names and contact information for study staff who can be reached for a phone or video conversation if they have any questions or concerns. We have received approval from clinical leadership for this approach. Interested intern physicians will be asked to click on a link in the email to open a secure RedCap survey. There, interns will again view an electronic copy of this information sheet. If the physician agrees to participate, he or she will click a button indicating "I agree". E-consent documentation (without signature or documentation of written consent) will be captured in REDCap, which is a secure, HIPAA-compliant web-based platform hosted on the MGB servers. We will provide sufficient information to the prospective provider-

subjects about the nature of the study and their rights within the fact sheet, as well as provide contact information for study staff and IRB for any additional questions.

BWH study staff and data analysts will track any physician turnover in the study using the Amion electronic residency scheduling system and the paging directory. While minimal turnover before the end of the block is expected, we expect any turnover to bias the trial results towards the null. If providers wish to revoke their consent and no longer participate in the study, they will also be removed from the study.

We also request a waiver of patient informed consent and authorization for the collection of routinely-collected patient data for outcome evaluation, given the minimal risk nature of the study, as we have done in prior work. We believe this waiver is justified as investigators will have no direct patient contact and all prescribing decisions are made under the care of licensed physicians, including supervising residents and attending who are directing their care. Finally, the intervention is exclusively provider-facing with the underlying goal of promoting patient safety in accordance with clinical practice guidelines.

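### The primary outcome counts only doses the study intern orders, but the objective and hypothesis concern doses prescribed to patients, and no all-prescriber version is defined to support a patient-level conclusion

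*Combined protocol and SAP*

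**What the plan says.** The primary objective in the Section 2 table is "To determine whether simulation-based training reduces the prescribing of high-risk medications to hospitalized older adults". Its endpoint is "Number of high-risk medications doses prescribed per day to eligible patients assigned to intervention providers compared with control providers". The null hypothesis in Section 7.1 uses the same patient-level terms: "number of high-risk medication doses prescribed per day to eligible patients assigned to intervention providers will be no different". Neither names who must have written the order.

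Section 6.2 opens in similar terms and then narrows the count: "We will only measure doses ordered by the interns in the study". Section 7.3.1 models the primary outcome without saying which of the two definitions is meant.

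The intern is not the only possible prescriber. Section 3.2 says of the teams: "These teams typically consist of an attending, a resident, an intern (i.e., 1st year of residency), and medical students". It also mentions day teams beside the twilight teams. Section 8.2 places prescribing decisions under the care of licensed physicians, "including supervising residents and attending who are directing their care".

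Three other provisions bear on the point:

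- Section 6.2 plans a secondary analysis of doses actually administered, in a new paragraph that names no prescriber.
- Section 6.2 also lists discharge on a high-risk medication as a secondary outcome, again without a prescriber limit.
- Section 3.2 says: "We will also measure subsequent prescribing for patients cared for by other providers". Neither Section 6.2 nor Section 7.3 takes this up.

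**The concern.** Doses ordered by the randomized intern and doses prescribed to the intern's patients are different quantities. They agree only if other prescribers' ordering for those patients does not respond to the intern's arm.

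There is a plausible route by which it could respond. Section 1 names pressure from nurses, patients and caregivers as a driver of these prescriptions. Training the intern does not remove that pressure, and Section 5.3 says interns know their arm. A request that a trained intern declines could go to the resident, the attending or the day team. The primary outcome would then fall while what the patient is prescribed stays the same.

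What is at stake is the wording of the conclusion. A positive primary result would support the statement that interns order less. The objective invites the wider statement that hospitalized older adults are prescribed less. Section 7.2 says the pilot is meant to inform larger evaluations, so the difference would carry forward.

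**Working it through.** **Inputs, all from Section 7.2:** 18 interns per arm; 36 patient-days per intern; difference 0.5 doses per patient-day; SD 1.1; correlation 0.2; two-sided alpha 0.05.

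**Step 1: reproduce the plan's power.**

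- Design effect = 1 + (36 − 1) × 0.2 = 8.0
- Effective patient-days per arm = 18 × 36 / 8.0 = 81
- SE of the difference = 1.1 × √(2/81) = 0.173
- Power = Φ(0.5/0.173 − 1.96) = 82.5%, or 80.2% using t on 34 df

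The plan's figure of more than 80% is reproduced on the patient-day reading. Counting the cluster as 12 patients gives 75.2%; that is a separate matter.

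**Step 2: let some orders move.** Suppose intern-ordered doses fall by 0.5 per patient-day and others re-order a share f of that fall. The reduction across all prescribers is 0.5 × (1 − f). The value of f is an assumption, so the whole range is shown. The last column gives the chance that an all-prescriber comparison is significant in favor of simulation, if SD and correlation stay as in Section 7.2.

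| f | Fall in intern orders | Fall in all orders to patients | Chance all-prescriber result is significant in favor |
|---|---|---|---|
| 0% | 0.5 | 0.5 | 82.5% |
| 10% | 0.5 | 0.45 | 74.0% |
| 25% | 0.5 | 0.375 | 58.3% |
| 50% | 0.5 | 0.25 | 30.4% |
| 75% | 0.5 | 0.125 | 10.8% |
| 100% | 0.5 | 0 | 2.5% |

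The intern-only outcome shows a fall of 0.5, with 82.5% power, in every row. It carries no information about f.

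**Step 3: precision of an all-prescriber estimate.** On the same assumptions, the 95% interval has half-width 1.96 × 0.173 = 0.34 doses per patient-day. An estimate of 0.25 would have an interval that includes 0. If the true difference were 0, the estimate would still favor simulation about half the time. Direction alone is therefore poor evidence.

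These figures use mean differences, as Section 7.2 does. Section 7.3.1 specifies a log-link Poisson model, which yields a rate ratio. The documents give no control-arm rate, so the differences cannot be converted to ratios.

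**The case against.** The intern-only count has a stated rationale. The objectives table justifies the endpoint because it "will provide evidence of provider behavior change during the follow-up period". Interns are the people randomized and trained, and Section 3.2 calls them the primary prescriber and first point of contact on the shifts where these drugs are typically started. Section 6.2 can be read as the working definition of a summary endpoint. This stands, and it is why the intern-ordered count can remain primary. It does not supply a measure for the patient-level objective.

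Shifting is also hypothetical. No section reports that interns hand orders on, and Section 3.2 excludes cross-coverage across teams. That stands too, although the exclusion does not reach the intern's own resident or attending, and day-team ordering for these patients is an inference. The discharge outcome has no prescriber limit and would pick up drugs started by anyone that persist to discharge. It is a yes/no measure at one time point and cannot replace doses during the stay.

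A reader might infer that nothing planned during the stay could reveal shifted orders. The text does not establish this. The administered-dose analysis states no prescriber scope, and the Section 3.8 footnote lists administration as an EHR field without one. Read patient-wide, it could show substitution in the doses patients actually receive. The supportable criticism is that its scope is unspecified.

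A reader might also take the Section 3.2 sentence on other providers as a promise of this analysis. Its wording can equally mean later prescribing, or prescribing to patients under other providers' care, and it sits in a sentence about use at scale. That it is left undefined is a smaller, separate point.

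**Conclusion.** The concern holds as a mismatch between the stated objective and hypothesis and the outcome that will be counted, with no defined all-prescriber outcome to bridge them. The intern-only result supports a conclusion about interns' own ordering. It supports a conclusion about prescribing to patients only if other prescribers do not make up the difference, and the plan does not commit to checking this.

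The size is conditional. With a fall of 0.5 in intern orders, the patient-level reduction lies between 0.5 (nothing shifted) and 0 (all shifted), and is half the observed effect at f = 50%. The documents do not place f within that range.

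It would be tempting to say that the trial has about an 80% chance of falsely declaring benefit. The documents do not support that. The figure is the planned power carried over to an assumed complete shift, with a full 0.5 fall in intern orders. Even then intern ordering would really have fallen; the error would lie in the interpretation, not in the test.

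**What to change.** 1. Keep intern-ordered doses as the primary outcome, and state that restriction in the Section 2 objectives table and in Section 7.1.
2. Pre-specify, as a key secondary analysis, the same GEE applied to high-risk doses ordered by any prescriber for the same eligible patient-days.
3. State in Section 6.2 that the administered-dose analysis covers doses from any prescriber.
4. Report the all-prescriber rate ratio with its confidence interval beside the primary result. Word the primary conclusion as a change in interns' own ordering. Base any statement about reduced prescribing to patients on the all-prescriber estimate and its interval, not on its direction alone.

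The cost is some wording and one extra model. Applying the intern-only filter already requires the ordering clinician for each order, so little new data should be needed. The downside is an all-prescriber estimate that may be noisier and smaller, and in a pilot of 36 interns may leave the patient-level question open.

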3.8 Schedule of activities

	Screening (7 days prior to rotation)	Randomization (2 days prior to rotation)	Day 2 of rotation	2-week follow-up
Review of general medical service schedule and outreach to eligible interns	X			
Completion of consent		X		
Completion of baseline questionnaire*		X		
Randomization		X		
Provision of interventions (simulation training and online education)			X	
Adverse event reporting measurement			X	X
Provision of endline (follow-up) questionnaire*				X
EHR and scheduling system data evaluation*				X

***Baseline Questionnaire (Providers):** Demographics (age, sex, race/ethnicity), 6-item State-Trait Anxiety Inventory³², 8-item Physicians' Reaction to Uncertainty Stress from Uncertainty subscale

Endline Questionnaire (Providers): 6-item State-Trait Anxiety Inventory³², 8-item Physicians' Reaction to Uncertainty Stress from Uncertainty subscale, Satisfaction with the interventions

EHR fields:

Baseline: Provider: Prior prescribing of high-risk medications; Eligible patients: Demographics (age, sex, race/ethnicity, insurance status), prior in-hospital use of one of the high-risk medications, admitted on one of the high-risk medications, hospitalization within last 30 days, total no. of home medications;

Follow-up: Prescribing of one of the high-risk medications, prescribing of albumin and other high-risk medications (e.g., opioids), discharge medication orders, administration of the one of the high-risk medications

Scheduling system (Amion®) fields:

Provider: Baseline; Prior inpatient service blocks (i.e., ICU service, ambulatory service), no. of months of internship, characteristics of the rest of the team (i.e., number of residents, seniority of attending, no. of other team members);
Follow-up: Completion of simulation training, no. of days on twilight service

4. Study Population

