The study will intervene upon physicians and their older adult patients admitted to the adult inpatient general internal medicine services at BWH and BWFH. We will focus on interns from the “twilight” (i.e., evening) teams as they cover the shifts during which the key high-risk medications of interest (specifically anti-psychotics, benzodiazepines, and sedative hypnotic “Z-drugs”) are typically first initiated and are also the first point of contact for nurses, pharmacists, and other physicians. Given their stage of training and nature of their workflow, they are also most prone to make decisions using System 1 thinking. We plan to exclude patients for the purposes of analysis who were on the relevant high-risk medication of interest prior to admission. For example, patients who were admitted on a benzodiazepine will not be included in the benzodiazepine/sedative hypnotic analysis but will be included in the antipsychotic analysis. Benzodiazepines and sedative hypnotics will be considered interchangeable for this analysis, due to the fact that they have overlapping indications. We will conduct stratified analyses by whether patients by whether they had exposed to one of the high-risk medications during their present admission prior to being under the care of the consenting intern.

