5.3 Measures to minimize bias: randomization and blinding

Interns who consent will be randomized in a 1:1 ratio to receive either intervention or control using a random number generator. We plan to conduct stratified randomization based on the service to which the intern is assigned to (GMS, ITU, or Faulkner).

The providers will not be blinded to which arm to which they were assigned, as blinding in the context of an intervention that is intended to motivate action will be infeasible. Physicians randomized to control will not have any way of accessing the intervention. Of note, once on a twilight team, interns are unlikely to rotate back onto a service, so contamination across arms should be minimal. Either way, if this does happen, they will not be re-randomized in the trial. Other ward staff and analysts will be blinded to arm assignment to the extent possible.

6. Study Assessments and Procedures

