7.3 Statistical analyses

7.3.1 *Analysis of the primary endpoint*

The unit of analysis is at the patient-level. We will evaluate the primary outcome using generalized estimating equations to adjust for physician-level clustering and multiple patient-day observations per physician using a log-link function, Poisson-distributed errors, and fixed effects for the treatment group and month of the year to account for seasonality. This approach will account for correlations between repeated measurements. Because this is a randomized trial, our primary analyses are planned as unadjusted; however, if there are strong predictors of the outcomes not balanced by stratified randomization, we will adjust for these in the primary analyses. We will conduct analyses using intention-to-treat principles. Given the nature of the data and how the outcomes are measured in EHR data, there will not be missing data for the primary outcome.

7.3.2 *Analysis of secondary endpoints*

We will use a similar approach for the secondary outcomes. For discharge medication orders (secondary outcome), we will also use generalized estimating equations that adjust for physician-level and patient-level clustering using a logit-link function, binary-distributed errors, and fixed effects for the treatment group and month of the year. For the outcomes measuring spillover

effects, the approach will be the same, except using a log-link function and Poisson-distributed errors. Given the nature of the data and how these outcomes are being measured primarily in EHR data, there should not be missing values. Because this is a randomized trial, our primary analyses are planned as unadjusted; however, if there are strong predictors of the outcomes not balanced by randomization, we will adjust for these in the primary analyses.

The implementation outcomes will be measured at the provider-level. The characteristics of consenting and non-consenting physicians will be measured descriptively, comparing the values using t-tests and chi-square tests or non-parametric analogs, as appropriate. Other implementation outcomes will be measured descriptively.

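### The primary model leaves adjustment for class eligibility and prior in-hospital exposure to an undefined imbalance trigger: no bias, but modest avoidable noise and a data-driven model

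*Combined protocol and SAP*

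**What the plan says.** **Outcome.** Section 6.2 counts doses per patient-day. For patients eligible for more than one class, "we will sum the medication doses across the classes".

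**Eligibility.** Section 4 (Study Population) applies the home-medication exclusion class by class: "patients who were admitted on a benzodiazepine will not be included in the benzodiazepine/sedative hypnotic analysis but will be included in the antipsychotic analysis". The plan pools hypnotics with benzodiazepines as one class, so a patient counts for one class or two.

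**Primary model.** Section 7.3.1 specifies a Poisson GEE with log link and "fixed effects for the treatment group and month of the year to account for seasonality". It says "our primary analyses are planned as unadjusted", then adds a condition: "if there are strong predictors of the outcomes not balanced by stratified randomization, we will adjust for these in the primary analyses".

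**Prior in-hospital exposure.** Section 4 plans a separate look: "We will conduct stratified analyses by whether patients by whether they had exposed to one of the high-risk medications during their present admission", counting exposure before the consenting intern took over.

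**Data and strata.** The baseline EHR fields in Section 3.8 include "prior in-hospital use of one of the high-risk medications, admitted on one of the high-risk medications". Section 5.3 stratifies only by service: "We plan to conduct stratified randomization based on the service to which the intern is assigned to" (GMS, ITU or Faulkner).

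**The concern.** A two-class patient can accrue doses that a one-class patient cannot, purely because of how the outcome is built. Prior exposure in the same admission is also a plausible strong predictor of further doses. Neither factor is a randomization stratum, a named covariate or an offset.

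The conditional clause does not settle this, for two reasons. First, it names no predictors and no threshold for imbalance, so the content of the primary model is decided after the data are seen. Section 7.3.3 compares baseline variables by arm but is not tied to any adjustment rule, and the imbalance check in Section 6.1 concerns provider characteristics. Second, a prognostic covariate improves precision even when the arms look alike, and an imbalance trigger gives up that gain.

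At stake are a little precision in a trial planned just above 80% power and a primary model that can be shown to have been fixed beforehand. Section 7 also gives no model for the class-specific or prior-exposure analyses that Section 4 mentions.

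**Working it through.** **Inputs from Section 7.2.** 18 interns per arm, 430 patients (215 per arm), 12 patients or 36 patient-days per intern, SD 1.1 (variance 1.21), correlation 0.2, target difference 0.5 doses per patient-day, two-sided alpha 0.05.

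**Assumed inputs.** The documents give neither the one-class/two-class split, nor the prevalence of prior exposure, nor the dose gaps. Assumed ranges, with q the share of patients and d the gap in doses/day:
- one-class patients: q = 0.3 to 0.5, d = 0.5
- previously exposed: q = 0.10 to 0.25, d = 1.0 to 1.5

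**Step 1: the plan's own figure.** Variance of an intern mean = 1.21 × (0.2 + 0.8/m).
- Day basis, m = 36: 0.2420 + 0.0269 = 0.2689. SE of the arm difference = √(2 × 0.2689/18) = 0.173. Power by a t test on 34 df is 80.2%, which reproduces the stated figure of over 80%.
- Patient basis, m = 12: 0.2420 + 0.0807 = 0.3227. SE = 0.189 and power is 72.8%, which does not reproduce it. That is a separate matter. Both bases are carried forward because the factors are patient-level.

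**Step 2: the ceiling.** A patient-level factor that varies by chance within interns can remove only the within-intern part: 0.0269/0.2689 = 10.0% on the day basis, 0.0807/0.3227 = 25.0% on the patient basis. Removing all of it leaves 0.2420 and a power of 84.2% on either basis.

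**Step 3: what each factor could remove.** Variance removed = q(1−q)d²/m, with the same m as in Step 1.

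| Factor (assumed) | q(1−q)d² | Day basis: removed, power | Patient basis: removed, power |
|---|---|---|---|
| None | – | –, 80.2% | –, 72.8% |
| Class, q 0.3, d 0.5 | 0.0525 | 0.0015, 80.5% | 0.0044, 73.3% |
| Class, q 0.5, d 0.5 | 0.0625 | 0.0017, 80.5% | 0.0052, 73.4% |
| Exposure, q 0.10, d 1.0 | 0.0900 | 0.0025, 80.6% | 0.0075, 73.8% |
| Exposure, q 0.25, d 1.5 | 0.4219 | 0.0117, 81.9% | 0.0352, 77.6% |

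Either factor alone therefore adds between about 0.3 and 5 points. With both at the top of their ranges and uncorrelated, q(1−q)d² sums to 0.4844. Power is then 82.2% on the day basis and 78.3% on the patient basis.

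**Step 4: chance imbalance.** SD of the shift in the arm difference = d × √(2q(1−q)/215), taking the factor as independent between patients. Class eligibility gives 0.022 to 0.024 doses/day and prior exposure 0.029 to 0.063. Against the patient-basis SE of 0.189 these are about 12–13% and 15–33%. This is random error already contained in the SE.

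**Step 5: cost of the extra terms.** The powers above keep 34 df. If three parameters reduced this to 31 df at the unadjusted SE of 0.173, power would be 80.0% rather than 80.2%. That is about the size of the day-basis gain from class eligibility.

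**Cross-check.** A small Poisson GEE simulation (300 runs per scenario; 50–80% two-class, 0–20% exposed with rate ratio 3, all assumed) gave SEs about 0.5–6% smaller and power about 1–3 points higher. Each simulated power has a Monte Carlo error of about √(0.8 × 0.2/300) = 2.3 points, so it supports the direction and rough scale only.

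**The case against.** The strongest reply is that the plan already deals with this. Section 7.3.1 allows adjustment of the primary analysis when strong predictors are unbalanced, prior exposure would plausibly qualify, and Section 4 plans analyses stratified by it. It would be wrong to say that the plan ignores these factors. What stands against the reply is narrower: the clause is undefined and reactive, and a stratified analysis does not sharpen the primary estimate.

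A reader might infer that pooling one-class and two-class patients biases the comparison. It does not: interns are randomized and the counting rule is identical in both arms. A reader might also infer that Sections 4 and 6.2 conflict. They fit together: Section 4 sets eligibility by class, and Section 6.2 says how to count when both classes apply.

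It is also fair to say that this is a pilot, that every prevalence and gap above is assumed, and that gaps of 1.0–1.5 doses/day are two to three times the target effect of 0.5. All of that stands and keeps the point minor.

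**Conclusion.** The point holds as a low-priority improvement. The primary outcome mixes one-class and two-class counts, and the model pre-specifies neither class eligibility nor prior exposure. Whether they enter is left to an undefined look at imbalance. The consequence is modest avoidable noise and a data-driven model choice, without bias.

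On consistent reckoning, either factor alone moves power from 80.2% to 80.5–81.9% (day basis) or from 72.8% to 73.3–77.6% (patient basis). Prior exposure supplies most of this; class eligibility alone is close to negligible. The figures rest on the assumed prevalences and gaps and on a difference-scale approximation to a log-link model.

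A reader might infer a larger gain by spreading the covariate over 12 patients but the residual over 36 days. That mixes two bases and can credit a factor with more than the 10.0% of variance lying within interns on the day basis; power cannot pass 84.2%. A larger gain would require the factors to explain differences between interns, and the documents give no evidence for that.

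**What to change.** In Section 7.3.1, replace the imbalance trigger, for these factors, with pre-specified fixed effects whatever the observed balance:

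1. Class eligibility at three levels: both classes, benzodiazepine/hypnotic only, antipsychotic only.
2. Any high-risk drug exposure earlier in the admission, dated before both the intern's care of the patient and the start of follow-up. Interns are randomized before the block and trained on Day 2, so the cut-off must exclude anything the randomized intern ordered.

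As a supportive analysis in Section 7.3, report the rate ratio for each class in its own eligible set, and carry over the prior-exposure stratification from Section 4. If the effect does not differ across these factors, the log-link rate ratio keeps its meaning after adjustment. If it does differ, the class-specific ratios will help to show it.

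The cost is SAP wording and three more parameters (two for class, one for exposure) in a 36-cluster GEE that already carries month effects. That cost is small but not zero. Both fields are already collected, so no new data or larger sample is needed.
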